### 8.2. POWER ANALYSIS

*For each confirmatory outcome, please provide power analyses demonstrating proposed sample sizes will be able to detect expected effect sizes for the outcomes targeted. Refer to previous studies of similar interventions for estimates of the required sample to inform power analyses. Note: If an impact evaluation is not proposed, this issue does not need to be addressed. You may use the table below to report the assumptions used in your power calculations, as well as the resulting minimum detectable impact for your confirmatory outcomes or provide them in the space below.*

Though not an RCT, the Power Analysis is as follows:

	Outcome 1:	Outcome 2:	Outcome 3:
Outcome Name	Parenting Attitudes	Father Relationship Behavior (parenting/co-parenting)	Father Financial Behavior
Continuous or binary?	Continuous	Continuous	Continuous

Level of significance (e.g., 0.05 percent)	0.05	0.05	0.05
Number of sides of test (one- or two-tailed)	2 tailed	2-tailed	2-tailed
Power (e.g., 80 percent)	80%	80%	80%
Total number of individuals in analytic sample	483	483	483
If continuous outcome, enter the standard deviation of the outcome (>0)	nFORM	nFORM	nFORM
Proportion of individual-level (or within-group) variance explained by covariates	nFORM	nFORM	nFORM
Minimum detectable effect size	0.030	0.030	0.030

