## 9.5. TRACKING PARTICIPANTS AND REDUCING ATTRITION

*If participants will complete post-program and/or follow-up surveys, please provide estimated response rates for each wave of data collection listed in 10.3. Please describe plans for tracking*

*participants and reducing attrition below. Note: If no post-program or follow-up surveys are proposed, this issue does not need to be addressed.*

For each wave of data collection listed in 10.3, what is your estimated response rate?	Baseline	T1: 100%-done at time of enrollment/orientation
	Wave 1	T2: 90%-Estimated completion rate
	Wave 2	T3: 70%-Estimated 1 year follow-up
	Wave 3	
	Wave 4	

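### The power table's minimum detectable effect of 0.030 does not follow from n = 483 with the planned paired t-test (about 0.13 SD of change), and the 483 is not tied to a survey wave

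*Protocol*

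**What the plan says.** The table in Protocol 8.2 has three columns: parenting attitudes, father relationship behavior (parenting and co-parenting), and father financial behavior. Every column is marked continuous, with alpha 0.05, a two-tailed test and 80% power. The row "Total number of individuals in analytic sample" reads 483 in each column, and the row "Minimum detectable effect size" reads 0.030 in each. The cells for the outcome's standard deviation and for the variance explained by covariates name only the data system, nFORM, and hold no number.

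Protocol 9.5 gives the expected response by wave: "T2: 90%-Estimated completion rate" for the exit survey and "T3: 70%-Estimated 1 year follow-up" for the one-year survey.

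SAP section 1 defines two samples. Attitudinal outcomes need an entrance and an exit survey; behavioral outcomes need an entrance and a follow-up survey. It adds that n will differ between outcomes, but names only missing data as the reason. Under its analytic approach, change is tested with paired t-tests, p-values are adjusted for multiple testing, and the binary account-ownership outcomes are reported as percentages. Protocol 9.1 describes financial behavior as two yes/no items, and the SAP's measure table classes the financial items as dichotomous.

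**The concern.** A minimum detectable effect of 0.030 is very small for a few hundred participants measured twice, and it is identical for three outcomes with different measures and time points. Protocol 1.2 labels all four research questions confirmatory, so this table is where a reader would look to judge what a null result means. Taking 0.030 at face value, that reader would conclude that a non-significant result argues against effects far smaller than the study can detect.

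The single 483 raises a smaller question. If exit and one-year response are 90% and 70% of the same enrolled group, the two expected sample sizes differ by a factor of 90/70 = 1.29, so one figure cannot be the expected n at both waves.

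**Working it through.** **Inputs.** n = 483, alpha 0.05 two-sided, power 80% and stated effect 0.030 (Protocol 8.2); response 90% at exit and 70% at one year (Protocol 9.5); paired t-test (SAP section 1, analytic approach). The enrolment target is not in the readable text. The SAP places the anticipated sample size in a CONSORT figure that is not reproduced in the copy reviewed.

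**1. Attempt to reproduce 0.030.** For a paired test, in SD units of the change score:

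MDES = (z₀.₉₇₅ + z₀.₈₀)/√n = (1.960 + 0.8416)/√483 = 2.8016/21.977 = 0.1275

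The noncentral t gives 0.1277. The stated figure is not reproduced; 0.1275/0.030 = 4.2.

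**2. Pairs needed for 0.030.** (2.8016/0.030)² = 93.39², about 8,720.

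**3. Power for 0.030 at 483.** The shift is 0.030 × 21.977 = 0.659. Power ≈ Φ(0.659 − 1.960) + Φ(−0.659 − 1.960) = 0.097 + 0.004, about 10%.

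**4. Other routes to 0.030 at n = 483.**

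| Variant | Result |
|---|---|
| One-sided paired test | 0.113 |
| Two equal groups, 483 in total | 0.255 |
| Covariate R² needed, paired test | 1 − (0.659/2.8016)² = 0.945 |
| Pre-post correlation needed, effect in raw SD units | 1 − (0.659/2.8016)²/2 = 0.972 |
| Slip for 0.30 | needs only (2.8016/0.30)² = 87.2, so 88 pairs |
| Omnibus regression f², 5 / 7 / 10 predictors | 0.027 / 0.030 / 0.034 |

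The f² route matches at about seven predictors, but that count is an assumption.

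**5. Does the choice of n explain 0.030?** Each row below is an assumption about what 483 means, with both response rates applied to all enrolled.

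| If 483 is | Enrolled | Exit n | MDES | One-year n | MDES |
|---|---|---|---|---|---|
| the one-year n | 483/0.70 = 690 | 0.90 × 690 = 621 | 0.112 | 483 | 0.127 |
| the exit n | 483/0.90 = 537 | 483 | 0.127 | 0.70 × 536.7 = 376 | 0.144 |
| the enrolled number | 483 | 0.90 × 483 = 435 | 0.134 | 0.70 × 483 = 338 | 0.152 |

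The range is 0.11 to 0.15, so no row comes near 0.030. These values apply to outcomes tested by paired t-test, which excludes financial behavior.

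**6. Multiplicity.** The SAP adjusts p-values but names no method. Assuming Bonferroni over four tests (alpha 0.0125), the multiplier is 2.4977 + 0.8416 = 3.3393. That gives 3.3393/√483 = 0.152 and 3.3393/√621 = 0.134.

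**The case against.** Three points on the other side have weight.

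First, the table names no effect metric. The SAP also lists a dosage model with covariates, and an f² near 0.03 is what an omnibus regression test could detect at 483 with about seven predictors. So 0.030 is not impossible in every metric. However, neither document says f² was meant or gives a predictor count, and the stated main analysis is the paired t-test.

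Second, a reader might infer that at least one of the three sample sizes must be wrong, or that the shared 483 is what makes the detectable effect wrong. The documents support neither inference. Because 483 is exactly 70% of 690, it may be the one-year n used as a cautious floor for every outcome; the exit n would then only be understated. The base of the 90% is also not stated outright. Protocol 9.5 calls it a completion rate, and the exit survey reaches only men present at the last session, whereas the one-year survey pursues everyone enrolled. Both rates are estimates. The 690 is back-calculated and should not be read as the plan's target. What stands is that the 483 is unlabelled.

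Third, the template in Protocol 8.2 waives a power analysis when no impact evaluation is proposed. Protocol 8.3 also records that evaluation enrolment ended on 4/12/2024, before the SAP of October 17, 2024. This limits the consequences, since no recruitment decision depends on the table, but a published precision figure should still be reproducible.

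**Conclusion.** The concern holds for the detectable effect. For the planned paired t-test, 0.030 is unsupported at n = 483: the figure is about 0.13 SD of the change score before multiplicity adjustment, and about 0.15 under the assumed Bonferroni correction over four tests. The table overstates precision roughly fourfold, and does so whichever wave 483 describes. This conclusion rests on the table's own alpha, sidedness and power, the SAP's choice of test, and an effect expressed in SD of change.

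The point about n is secondary and is one of labelling. Exit and one-year outcomes share 483 with no wave or floor stated, and the difference this makes to precision is a factor of √1.29 = 1.13 if both rates share one base.

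For financial behavior, neither 0.030 nor 0.13 is meaningful as a paired-t effect: the outcome is binary, and the SAP reports it descriptively. Its continuous label in the power table conflicts with Protocol 9.1 and the SAP.

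**What to change.** In the Protocol 8.2 table:

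- Replace 0.030 with the detectable effect for the paired test, stating the metric and the SD used. At n = 483 this is about 0.13 SD of the change score before multiplicity adjustment and somewhat larger after it. Name the adjustment method if the adjusted value is given. If 0.030 was meant in another metric, state the metric, the model and the number of predictors.
- Give n by wave, or label 483 as the minimum across outcomes. If the team confirms that 483 is the one-year n (690 enrolled), the exit entry for attitudes would be about 621, with a detectable effect of about 0.11.
- Change financial behavior from continuous to dichotomous. Either omit a detectable effect, since the outcome is only described, or give one for a change in a paired proportion.

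The cost is an edit to one table; enrolment, data collection and the planned tests do not change.

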## 9. DATA COLLECTION

### 9.1. CONSTRUCTS AND MEASURES

*Clearly articulate the constructs of interest, measures to evaluate those constructs, and specific data collection instruments. Provide any information on the reliability and validity of the data collection instruments. For standardized instruments, you may provide the citation for the instrument.*

Construct	Measure	Instrument	Reliability and Validity (if standardized instrument, you provide a citation for the instrument)
Parenting Behavior (interaction with children)	1 item: hours spent w/children in last 30 days (interval); 1 item: frequency reach out to children (categories, 5-point scale); 7 items: frequency engage in key behaviors (categories, 5-point scale)	nFORM Community-Based Fathers Survey (A2b, A2c, A5b: b-d, f-i)  *also asked on OLLE; will use data from survey with the most complete data	n/a

Co-Parenting Behavior	11 items: frequency of agreement with key co-parenting behaviors (interval, 5-point scale)	nFORM Community-Based Fathers Survey (A13: a-k)  *also asked on OLLE; will use data from survey with the most complete data	n/a
Father Financial Behavior	2 items: yes or no questions for have resume, checking/savings accounts (dichotomous)	nFORM Community-Based Fathers Survey (B3, B3a)  *also asked on OLLE; will use data from survey with the most complete data	n/a
Parenting Attitudes (toward children)	7 items: frequency of key attitudes (categories, 5-point scale)	nFORM Community-Based Fathers Survey (A3: a-g)  *also asked on OLLE; will use data from survey with the most complete data	n/a

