All in Dads! Healthy Marriage and Responsible
Fatherhood Program Evaluation

Statistical Analysis Plan

NCT05194020

October 17, 2024

1. Data Analysis

Briefly describe the planned approach for data analysis. If an impact analysis is proposed, name the key dependent and independent variables, and describe any methods to minimize Type I error (i.e., finding positive impacts by chance) such as limiting the number of impacts to be analyzed and/or multiple comparison correction. Describe proposed approach(es) for addressing missing data.

Identify study sample

The study sample includes participants who: 1) gave recorded informed consent to be part of the study, and 2) took both an entrance and exit survey (for attitudinal outcomes) or entrance and follow-up survey (for behavioral outcomes). The CONSORT diagram in Figure 2 shows exclusion criteria and the anticipated size of the overall study sample. The analytic sample for particular outcome measures will vary based on missing data.

Defining analysis measures

For each outcome construct, we have identified the relevant measures from nFORM that are theoretically aligned with that construct. We will generate a correlation matrix between items in a given construct to ensure that theoretically related items are also empirically related in our data set. Items that are not strongly correlated with other items in a construct will be removed as necessary. Factor analysis will be used to ensure that all construct items hang together (using an alpha of 0.7 or higher as the threshold). If an alpha of 0.7 cannot be obtained, that outcome will be removed.

Once we are confident that all of the items align with a given construct, we will create a composite measure by taking an average of the scores on each non-missing item in the construct. The measure definition matrix below provides information on each proposed outcome. For composite measures, a change score will be calculated between a participant's pre-program composite score and post-program composite score. For standalone survey items, a change score will be calculated between a participant's pre-survey and post-survey responses.

For the sake of consistency and simplicity, parenting and co-parenting analyses will use a participant's youngest child as the focal child.

Model Specification to Predict Outcomes With Dosage

Construct by Outcome	Dependent Variables (follow-up)	Response Codes for Dependent Variables	Dependent Variable Type	Independent Variables

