Missing data for the implementation outcomes could happen as a result of programmatic data entry issues. For the sake of this evaluation, we assume that any primary or support services received by a participant are being accurately logged into nFORM, so a lack of documented attendance, service contacts, referrals, etc. is indicative of lack of services (i.e., a participant not receiving the program components as intended).

Assessing non-response bias

We will conduct response rate analysis for each primary outcome of interest to assess non-response bias and adjust for threats to internal validity. Using data from the Applicant Characteristics Survey, we will look at demographics (race, ethnicity, age, education level) and primary reason for joining the program among participants who fall into each of the following categories: 1) non-respondents who answered no surveys after the ACS, 2) respondents who completed the pre-survey only, 3) respondents who completed the post-survey only, and 4) respondents who completed both the pre- and post-survey (complete case).

Analytic approach

The main goal of this descriptive study is to assess pre-post change scores in the attitudinal outcomes listed above and assess pre-to-one-year follow-up change scores in the behavioral outcomes listed above among program participants before and after primary workshops. We will use paired sample t-tests to assess the magnitude and significance of changes among program participants in the analytic sample for each outcome. For binary economic stability outcomes, we will descriptively report the percent of participants who opened a checking or savings account one year after enrollment, compared to the percent who had opened these accounts before the program. We will adjust our p-values for multiple hypothesis testing and report the adjusted p-values in the appendix of the final report.

2. Data Archiving and Transfer

Briefly describe the planned approach data arching and transfer by addressing questions below.

What procedures and parameters are established for all aspects of data/information collection necessary to support archiving data collected as part of the evaluation?

Examples include informed consent, data maintenance, de-identifying data procedures.

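### The stated minimum detectable effect size of 0.030 has no unit and does not match the planned paired t-test, which detects about 0.13 SD of change at n = 483

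*Protocol*

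**What the plan says.** Protocol Section 8.2 has three outcome columns: Parenting Attitudes, Father Relationship Behavior (parenting and co-parenting) and Father Financial Behavior. All three are labelled continuous and share the same inputs: alpha 0.05, two-tailed, 80% power, and 483 in the row headed "Total number of individuals in analytic sample". The rows for the outcome SD and for the variance explained by covariates hold only the name of the data system (nFORM). The last row reads "Minimum detectable effect size 0.030 0.030 0.030", with no unit.

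The SAP, under Analytic approach, gives the main method: "We will use paired sample t-tests to assess the magnitude and significance of changes". It adds "We will adjust our p-values for multiple hypothesis testing" without naming a procedure. For the binary financial items it says "we will descriptively report the percent of participants who opened a checking or savings account one year after enrollment". Under Identify study sample it notes: "The analytic sample for particular outcome measures will vary based on missing data".

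Protocol Section 9.1 defines the financial measure as "2 items: yes or no questions for have resume, checking/savings accounts (dichotomous"), and the SAP's measure table also types the financial items as dichotomous. That table is headed "Model Specification to Predict Outcomes With Dosage" and lists hours of attendance and baseline covariates as independent variables. It does not count the predictors.

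**The concern.** A minimum detectable effect follows from the sample size, alpha, power and test, expressed in a stated unit. Here the first three are given, the test is in the SAP and the unit is missing. For a one-group paired comparison of 483 people, 0.030 looks far too small.

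Section 8.2 is the plan's only statement of what the pre-post comparisons can detect, and Section 1.2 marks all four research questions as confirmatory. A reader who takes 0.030 as a standardised change would conclude that a non-significant result makes any change above 0.03 SD unlikely. If the true sensitivity is several times coarser, that reading of a null result is wrong.

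**Working it through.** **Inputs.** From Section 8.2: n = 483, two-sided alpha 0.05, power 0.80. From the SAP: paired t-test on the change score. Because 483 is labelled the analytic sample, no attrition is deducted.

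**Step 1: the paired t-test.** In units of the SD of the change score,

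MDES = (z₀.₉₇₅ + z₀.₈₀) / √n = 2.8016 / √483 = 2.8016 / 21.977 = 0.1275.

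The exact noncentral t calculation gives 0.1277. The stated 0.030 is not reproduced: 0.1277 / 0.030 = 4.26.

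**Step 2: power at n = 483 (noncentral t, two-sided).**

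| True change (SD of change) | Power |
|---|---|
| 0.030 | 10% |
| 0.05 | 20% |
| 0.10 | 59% |
| 0.13 | 81% |

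Pairs needed for 80% power at 0.030: (2.8016 / 0.030)² ≈ 8,721, or 8,723 by noncentral t.

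**Step 3: could 0.030 be right in another unit?**

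- *SD of the raw outcome.* With equal variances and pre-post correlation ρ, MDES = 0.1277 × √(2(1 − ρ)). The documents give no ρ. Assumed values of 0.3, 0.5, 0.7, 0.8 and 0.9 give 0.151, 0.128, 0.099, 0.081 and 0.057. Reaching 0.030 needs ρ = 1 − (0.030 / 0.1277)² / 2 = 0.972.
- *Raw scale points.* The SD of change would have to be 0.030 / 0.1277 = 0.235 points. No SD is given.
- *Misplaced decimal for 0.30.* A paired test of 0.30 SD of change needs only about 90 pairs, so 0.30 is not the paired MDES at 483.
- *Cohen's f-squared in a regression.* At N = 483 and 80% power, a joint test of 1, 5, 7 or 10 predictors detects f-squared of 0.0163, 0.0269, 0.0302 or 0.0343. With seven predictors, power at 0.030 is 0.798. This is a near match, but it depends on a predictor count and a metric that appear in neither document. It would describe the SAP's dosage-and-covariate model, whereas R1 to R4 ask whether outcomes improve after baseline.

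**Step 4: the third column.** Section 8.2 says continuous; Section 9.1 and the SAP table say dichotomous; the SAP plans descriptive percentages. A continuous MDES therefore does not apply to Father Financial Behavior, whatever unit 0.030 is in.

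**Step 5: sensitivity to points the table leaves open (assumptions, not plan figures).**

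- *Multiplicity.* Under Bonferroni for three, four or five tests, the MDES at n = 483 is 0.148, 0.152 or 0.156.
- *Different waves.* Attitudes are compared at exit and behaviors at one year, and Section 9.5 expects 90% and 70% response. If 483 is the one-year number, exit would have 483 × 0.90 / 0.70 = 621 (MDES 0.113). If 483 is the exit number, one year would have 483 × 0.70 / 0.90 ≈ 376 (MDES 0.145).

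**The case against.** The strongest reply is that little depends on this table. The Section 8.2 template waives power analysis when no impact evaluation is proposed, and the study is descriptive. Study enrolment was set by calendar dates and, according to Section 8.3, had ended before the SAP was dated, so a new figure cannot change the sample. The report's estimates and their precision will show how informative a null result is. This stands, and it limits the consequence to how the plan and its null results are read. It does not make a figure that the sponsor chose to publish correct.

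A second reply is that an arithmetic slip is unproven. With no metric stated, 0.030 could be a sound f-squared value missing its label. A two-group formula with 70% of 483 (338) gives 2 × 2.8016 / √338 = 0.305, so a slipped decimal from such a calculation is also conceivable. The origin is indeed unsettled. But the first reading needs an unstated metric and predictor count. The second needs a comparison group that the design lacks and a deduction from a number already labelled analytic. Neither makes 0.030 the sensitivity of the planned paired tests.

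Third, the Bonferroni and response-rate figures rest on assumptions, and the CONSORT diagram that gives the anticipated sample size cannot be seen in the text reviewed. That is fair: they illustrate a range, and the main result does not depend on them.

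**Conclusion.** The concern holds. For the continuous outcomes, the stated inputs and the SAP's paired t-test give a minimum detectable effect of about 0.13 SD of the change score, against 0.030 stated without a unit. This needs no assumption beyond taking 483 as the number of analysed pairs, as the table labels it. The 10% power figure applies if 0.030 is read as SD of change. Converting 0.13 to outcome SD or scale points needs a correlation and an SD that the documents do not give. Where 0.030 came from cannot be determined. The continuous label on Father Financial Behavior is a separate inconsistency that stands under any reading. The corrected 0.13 is still a small effect, so the design is not undermined; only its stated sensitivity is wrong.

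**What to change.** In Section 8.2:

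1. For the continuous outcomes, replace 0.030 with about 0.13 SD of the change score at n = 483, and name the paired t-test and the unit.
2. If the analysed number differs between exit and one-year outcomes, give each its own n and MDES.
3. If 0.030 came from another metric, such as f-squared for the dosage model, label it, state the predictor count, and keep it apart from the sensitivity of the pre-post tests.
4. Name the p-value adjustment and add the MDES at the adjusted alpha (about 0.15 to 0.16 under Bonferroni for three to five tests).
5. Remove the continuous MDES for Father Financial Behavior, or replace it with a paired-binary calculation if a test is intended for R3.

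The cost is a table correction and a less favourable stated sensitivity. Enrolment, surveys and conduct are unaffected.
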